#### 8. **EFFICACY**

#### 8.1. **Hypotheses**

There are 3 possible pairwise comparisons among the treatment arms for the efficacy endpoints. Only treatment versus placebo comparisons will be shown. The two comparisons are of principal interest and will be conducted for superiority: brensocatib 10 mg vs placebo and brensocatib 25 mg vs placebo. The corresponding null  $(H_0)$  and alternative  $(H_1)$ hypotheses for the primary endpoint are:

1. 
$$H_{01}$$
:  $\frac{\lambda_{10 mg}}{\lambda_{Placebo}} = 1$  vs  $H_{11}$ :  $\frac{\lambda_{10 mg}}{\lambda_{Placebo}} \neq 1$   
2.  $H_{02}$ :  $\frac{\lambda_{25 mg}}{\lambda_{Placebo}} = 1$  vs  $H_{12}$ :  $\frac{\lambda_{25 mg}}{\lambda_{Placebo}} \neq 1$ 

2. 
$$H_{02}$$
:  $\frac{\lambda_{25 mg}}{\lambda_{Placebo}} = 1$  vs  $H_{12}$ :  $\frac{\lambda_{25 mg}}{\lambda_{Placebo}} \neq 1$ 

where  $\lambda$  represents the mean rate of pulmonary exacerbations. The null (H0.) and alternative (H1) hypotheses for testing of the secondary endpoints are defined similarly. All superiority comparisons will be two-sided with test-specific alpha as per the multiple testing procedure described in Section 6.3.

#### **8.2.** Primary Endpoint - Annualized Rate of Pulmonary **Exacerbations**

The primary efficacy endpoint is the Annualized Rate of PEs (including severe PEs) that have been confirmed through the event adjudication process (see Section 6.7.1).

#### 8.2.1. **Main Analyses**

The Primary Estimand is the On-Study Estimand in which all observed data up to Week 52 will be included in the analysis (see Section 2). The ITT Analysis Set (see Section 5.2) will be used for this Estimand.

The Annualized Rate of PEs will be analyzed using negative binomial regression as implemented in SAS® PROC GENMOD with robust estimate for the covariance matrix. The latter will be achieved by introducing a REPEATED-Statement identifying participant-ID with TYPE=UNSTR^4 for the covariance as unstructured. The model will include treatment group and the randomization stratification factors (sputum sample being classified as positive or negative for *Pseudomonas aeruginosa* at Screening Visit, the number of prior PEs [<3 or ≥3] in the previous 12 months, stratification region [North America, Europe, Japan, and the Rest of the World]), and age group (adult, adolescent) as fixed effects. If the age group covariate creates estimability issues, it may be removed. If the model still does not converge after removing the age group covariate, other handling including using the parametric covariance estimator instead of the robust sandwich covariance estimator may be applied. The time at risk in years (log scale) will be included in the model as an offset variable. The LOG-link function will be used in the model. The OM option will be used to adjust the co-

**CONFIDENTIAL** Page 52 of 139

<sup>4 TYPE=UNSTR option specifies that the covariance matrix of the scores be estimated empirically.

efficients for the LSMEANS to reflect the observed data. An example SAS code can be found in Appendix I.

The annualized Rate of PE for each treatment group, the ratios of PE rates between each brensocatib dose and placebo, and the associated 95% Cis will be estimated from the negative binomial model. In addition, the frequency distribution of participants experiencing 0, 1, 2, 3, and >=4 exacerbations will be provided.

Occurrence of exacerbation events that meet the protocol definition of PE diagnosis based on independent adjudication process will be explored graphically. The below histograms will be produced. Treatment groups will be distinguished by separate bars.

- Count of PEs reported every month in study starting at Day 1 through Week 52. Differentiation of PEs into study month is detailed in Section 6.7.1.7.
- Mean Cumulative Function of PEs reported starting at Day 1 through Week 52 will be created (see Appendix I for technical details)
- Count of PEs within the categories: "0", "1", "2", and ">=3"

### 8.2.2. Sensitivity Analyses – Tipping Point

If there are study participants who discontinue randomized IP early and decline to remain in the study, ascertainment of data will be incomplete, and a true Treatment Policy/ITT analysis cannot be achieved. A "missing at random" (MAR) assumption for the missing data is made implicitly for the On-Study Estimand.

The main analysis using the negative binomial model is unbiased under the MAR assumption for the missing data. However, in some instances, the fact that data are missing may be directly related to the unobserved values, i.e., missing not at random (MNAR). Therefore, robustness of the main analysis to departures from the MAR assumption will be assessed using tipping-point analyses. Due to the inherent difficulties in identifying the missing data mechanism in practice, all missing data will be assumed MNAR, and the tipping point penalties will be applied accordingly.

As the first step, multiple imputations (MI) of missing PE data under the observed data model (MAR assumption) will be implemented using negative binomial model, which models the distribution of a response Y, e.g., the number of PE events, as the joint distribution of the observed responses  $Y_{obs}$  and a distribution of the missing responses  $Y_{mis}$  after discontinuation from the study. Missing post withdrawal PEs will be imputed with the predicted PE values from the model, per treatment and strata, for the time remaining after study discontinuation prior to Week 52. Refer to Figure 2 as a visualization of the different periods of a participant's participation who discontinued early from study.

Figure 2: Sensitivity Analysis: Period of Discontinued Participants

CONFIDENTIAL Page 53 of 139

For a given participant, the conditional distribution  $Y_{mis}|Y_{obs}$  is a function of the observed events  $y_1$ , the estimated dispersion, the estimated PE rate in period 1 (which is the same as obtained in the primary analysis) and the model covariates. The imputed count of PEs will be combined with the observed PE count. The process of imputing missing PE data will be repeated multiple times to create 100 separate datasets.

As the second step, a penalty (delta) will be applied to the imputed data prior to analyzing each of the separate data sets. For each brensocatib dose comparison relative to placebo, the tipping point penalties (delta adjustment) will be applied in a bi-directional manner. That is, the PE rate (after imputation) for the MNAR data in the brensocatib arms will be incrementally increased, while the PE rate for the MNAR data in the placebo arm will be incrementally decreased. With each increment, the 100 complete data sets will each be analyzed using the same model as for the primary analysis. The analysis results for each increment will be combined using Rubin's rules (Rubin 1987).

This process of incrementing the penalties will continue until the respective comparison is no longer statistically significant at two-sided  $\alpha$ = 0.01 (i.e., the Tipping Point) per the multiple testing procedure described in Section 6.3 or until the PE rate has been incremented until 3-fold the observed reduction has been achieved.

The delta penalties to be investigated are pre-selected multiples of the observed rate reduction. If the observed rate ratio reduction from the primary analysis is x, the deltas to be investigated will range from 1-x to 1+3\*x for both active and the placebo arms, in increments of 0.5\*x (for example, if the observed rate reduction is 30% [x=0.3] the imputed rates will be multiplied by deltas of 0.7 to 1.9 in increments of 0.15) as shown in Table 7. The increment or range may be refined based on analysis results and the location of tipping point.

The grid below provides an example of the bi-directional delta increment/decrement for the comparison of brensocatib 25 mg vs placebo. Note, some of the intermediary cells (delta increments) have been eliminated for brevity. The post-withdrawal mean rate is calculated as the delta\*mean rate under the MAR assumption (where z=mean rate under MAR assumption for brensocatib 25 mg; y=mean rate under MAR assumption for placebo). The cell with delta = 1 for both brensocatib 25 mg and placebo represents the primary analysis result under MAR (see Section 8.2.1).

Table 7: Primary Endpoint: Tipping Point Analysis – Delta Increment / Decrement

				В	rensocatib	25 mg		
				Delta				
			0.70	1.00	1.30	1.60	1.90	
	Delta	Mean Rate						
		Post	(1-x)*z	1*z	(1+x)*z	(1+2*x)*z	(1+3*x)*z	
		Withdrawal						
Dlaasha	1.90	(1+3*x)*y						
Placebo	1.60	(1+2*x)*y						
	1.30	(1+x)*y						
	1.00	1*y						
	0.70	(1-x)*y						

Some of the intermediate steps left out for brevity.

CONFIDENTIAL Page 54 of 139

For each of the above cells, complete sets of exacerbation data (observed and imputed) for the 3 treatment arms will be generated using multiple imputation under the MAR assumption. The imputation model will contain the same covariates as in the primary analysis model (Section 8.2.1). Missing data are assumed to be MNAR and will then have the corresponding delta applied. One hundred (100) separate complete data sets for each of the relevant cells will be generated and analyzed. The log-scale results will be combined using Rubin's method (Rubin 1987) and then exponentiated to obtain final estimates for the rates and rate ratios. The relevant delta increment/decrement grid for each brensocatib dose comparison will be populated with the corresponding p-values. Should a Tipping Point be identified, the plausibility of the assumptions surrounding the MNAR data (i.e., magnitude of the delta adjustments in both treatment arms) will be assessed from a clinical perspective.

Technical details for the implementation in SAS can be found in Appendix I.

## 8.2.3. Supplementary Analyses – Time at Risk Replaced by the Total Time on Study

A supplementary analysis will be performed by repeating the primary analysis and redefining participants time at risk. Time at risk will be the participants total time on study:

- Date of EOT date of randomization + 1: for participants completing 52 weeks of treatment period;
- For participants who discontinue from treatment and study at the same time: Date of EOS/discontinuation date of randomization + 1.
  - For participants who discontinue from treatment but remain in the study, the minimum duration between date of randomization and the (theoretical) date of Week 52:

364 (day) or

the date of EOS/discontinuation – date of randomization  $+\ 1$ 

will be used for the On-Study Estimand.

The duration of PEs will be ignored in this analysis.

#### 8.2.4. Sensitivity Analyses – Reference-Based-Multiple-Imputation

A Jump-to-Reference sensitivity analysis will be performed where the Placebo arm will act as the reference arm. All data with an assessment or visit date prior to the time of the first of any ICE (see Section 2) will be included. Data with an assessment or visit date after occurrence of an ICE related to treatment failure (e.g., early discontinuation from randomized treatment for lack of efficacy, treatment discontinuation due to AE, or start of additional chronic antibiotics) will be considered missing and imputed.

Multiple imputations will be used to replace missing outcomes for brensocatib- and placebotreated study participants.

To note, the need for this sensitivity analysis will be evaluated during the BDRM prior to database lock and unblinding of the study. It will be conducted and included in the CSR if there are a non-trivial number of ICEs related to treatment failure.

CONFIDENTIAL Page 55 of 139

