#### 2. STUDY OBJECTIVES AND ESTIMANDS

The treatment effect of brensocatib will be evaluated using the On-Study Estimands primarily; supported using the On-Investigational Product (IP) and On-Treatment Estimands. The treatment regimen in the On-Study Estimand is the randomized assignment to IP irrespective of discontinuation or modifications to standard of care. The On-Study Estimand provides a pragmatic assessment of brensocatib's effectiveness. The treatment regimen for the On-IP estimand is the randomized IP irrespective of modifications to standard of care. The treatment regimen for the On-Treatment Estimand is the randomized IP plus standard of care without addition of new chronic antibiotics during the treatment period or modifications to chronic antibiotics taken at baseline. The On-Treatment estimand describes brensocatib's efficacy.

Note, chronic treatment with antibiotics is permitted for all Estimands if such treatment was initiated at least 3 months prior to Screening. For this study, standard of care is equal to being on a chronic course of antibiotics without any changes in dose nor administration route at baseline. About 20% of participants are on chronic treatment with antibiotics.

The On-Treatment assessment of efficacy is considered supplementary, and will be important in describing the risk:benefit and cost-effectiveness. For this Estimand, the intercurrent event (ICE) of initiation of a new chronic antibiotic during the 52-week treatment period will be defined as any antibiotic intake for more than 28 days other than for the treatment of a concurrent pulmonary exacerbation. Discontinuation from a baseline chronic antibiotic during the 52-week treatment period is also an ICE for the On-Treatment estimand as this can impact the assessment of efficacy. Further, participants randomized but not treated will be excluded from any statistical analysis and data tabulation.

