The Composite Estimand will be utilized as a supplementary assessment of responder status for whether participants are exacerbation free over the 52-week treatment period. Participants who experience ICEs associated with treatment failure (i.e., addition of a new chronic antibiotic during the treatment period, early discontinuation of IP due to lack of efficacy, early discontinuation of IP due to a treatment-related adverse event (AE), or death due to Non-Cystic Fibrosis Bronchiectasis [NCFBE]) will be considered as "non-responder" for the endpoint. ICEs of early discontinuation of IP for other reasons will be handled using the Treatment Policy strategy per the International Council for Harmonisation (ICH) E9(R1) Addendum.

CONFIDENTIAL Page 13 of 139

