## **6.2.** Considerations for Constructing Estimands

Analysis of the On-Study Estimands will be conducted in the ITT Analysis Set (see Section 5.2) in which all observed data will be included regardless of whether the participants remain on randomized IP. This Estimand will be considered the Primary Estimand and utilizes the Treatment Policy strategy for ICEs (see Section 2). Analyses of the On-IP and On-Treatment Estimands will be conducted using the ITT Analysis Set for efficacy endpoints.

For all On-Study Estimands for the primary and secondary endpoints in the multiple testing procedure, tipping point sensitivity analysis will only be conducted if the main results are statistically significant.

A blinded data review meeting (BDRM) will be conducted to review the definition of analysis sets, the assignment of participants into the analysis sets, as well participants meeting criteria for ICEs of the study Estimands (see Section 2). A data review report (DRR) will be prepared and signed prior to database lock and unblinding to document participant's assignment into analysis sets and agreed actions for participants meeting any ICE criteria prior to database lock and unblinding. Any incorrect treatment assignments determined subsequent to database lock and unblinding will be included in the DRR minutes as an addendum.

Analysis details are presented in Section 9.

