#### 6.7.2. Responder Status for Exacerbation-Free over the 52-Week Treatment Period

For the On-Study Estimand, a participant will be defined as "Responder" / "Non-responder" based on exacerbation events that are confirmed through adjudication over the 52-week treatment period.

In order, to be a "Responder" participants must:

- complete 52-Weeks on study, AND
- have no exacerbation event that meets the protocol definition of PE diagnosis confirmed by an independent adjudication committee during the 52-Weeks.

If a participant has at least one PE confirmed through adjudication during the 52-Week study period, the participant will be classified as "*Non-responder*".

CONFIDENTIAL Page 41 of 139

For participants who discontinue the study prior to Week 52 without having experienced a PE confirmed through adjudication, their responder status will be imputed based on the observed data model (see Section 8.3.2.1).

For the Composite Estimand, the above criteria must be met, at a minimum, in order to be classified as "*Responder*". However, participants meeting one of the below criteria will be considered as "*Non-responder*", given no PE was observed prior to:

- Early discontinuation from randomized IP for the below reasons:
  - o Death due to NCFBE (to be investigated through the AE page)
  - Lack of efficacy
  - Tolerability; defined as discontinuation from randomized IP due to an AE which is deemed to be related to the randomized IP by the investigator; cases will be identified through the AE eCRF by looking for action="DRUG WITHDRAWN", relationship="RELATED"
- Addition of chronic antibiotics over the 52-Week Treatment Period

Early discontinuation from randomized IP for other reasons will follow the Treatment Policy strategy.

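### SAP 8.2.4 includes data up to the first of any intercurrent event but imputes only after treatment-failure events, so read literally the Jump-to-Reference analysis drops other observed follow-up and is not a reliable stress test of the primary result

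*SAP*

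**What the plan says.** SAP 8.2.4 plans a Jump-to-Reference analysis of the annualized exacerbation rate, with placebo as reference. Its inclusion rule is: "All data with an assessment or visit date prior to the time of the first of any ICE (see Section 2) will be included". Its missing-data rule is narrower. "Data with an assessment or visit date after occurrence of an ICE related to treatment failure" is treated as missing and imputed, and the examples given are "early discontinuation from randomized treatment for lack of efficacy, treatment discontinuation due to AE, or start of additional chronic antibiotics". A further sentence says that missing outcomes in all arms will be multiply imputed, without saying which outcomes. The analysis runs only if the blinded data review finds a non-trivial number of failure-related ICEs.

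Not every ICE is a treatment failure. Investigational product (IP) can be stopped for other reasons, and SAP Section 2 adds: "Discontinuation from a baseline chronic antibiotic during the 52-week treatment period is also an ICE for the On-Treatment estimand". The same section puts about 20% of participants on chronic antibiotics.

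The On-Study estimand, which this analysis is meant to probe, uses the ITT set "in which all observed data will be included regardless of whether the participants remain on randomized IP" (SAP 6.2). SAP 6.6 says that data after IP discontinuation are collected to allow full ascertainment for that estimand.

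Treatment failure is also listed in Section 2 and 6.7.2, for the Composite Estimand of the exacerbation-free endpoint. There the adverse-event criterion is "discontinuation from randomized IP due to an AE which is deemed to be related to the randomized IP by the investigator", death due to bronchiectasis is named, and "ICEs of early discontinuation of IP for other reasons will be handled using the Treatment Policy strategy".

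**The concern.** The two rules in 8.2.4 do not meet. Data after a non-failure ICE lie outside the inclusion rule and outside the imputation rule. A programmer who follows the text would end those participants' counts and time at risk at the ICE, although their later exacerbations were observed.

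Nothing else in the SAP settles the matter. Table 5 defines event inclusion and time at risk for the On-Study, On-Treatment and On-IP estimands only. Appendix I details the tipping-point imputation but has no Jump-to-Reference section. Protocol 10.4.6.1.3 left the full details of the sensitivity analyses to the SAP.

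What is at stake is interpretation. Post-discontinuation follow-up on brensocatib is where a diluted effect would show. If it is discarded and not replaced, the analysis can return a ratio better than the primary, and that could be read as robustness. In addition, treatment failure is given only by example in 8.2.4, yet it governs both the data selection and whether the analysis is run.

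**Working it through.** **1. The plan's own figure.** Section 8.2.4 states none. The nearest is the 90% power in SAP 3.2: 540 per arm, placebo rate 1.2, dispersion 1, rate ratio 0.70 (so 0.84 on brensocatib).

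- SE(log ratio) = √{[(1/1.2 + 1) + (1/0.84 + 1)]/540} = √(4.0238/540) = 0.0863.
- Expected z = −ln(0.70)/0.0863 = 4.13.
- At two-sided 0.005 per comparison (protocol 10.1), power is 90.7%.

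The figure reproduces per comparison, and the present point does not affect it. The rates and the SE are used below.

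**2. Assumptions not in the documents.** In each arm a share d = 10–20% has an ICE, at mid-year on average, so f = d/2 of person-time is post-ICE. A share s = 1/3 to 1/2 of ICEs is failure-related. Everyone stays on study. Placebo stays at 1.2 after an ICE. The brensocatib rate after an ICE is r: 1.2 (effect lost), 1.02 (halfway) or 0.84 (effect kept).

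**3. Formulas for the expected rate ratio.**

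- Primary: [0.84(1 − f) + r f]/1.2
- 8.2.4 read literally: [0.84(1 − f) + 1.2 f s]/{1.2[1 − f(1 − s)]}, which does not depend on r
- Non-failure follow-up kept: [0.84(1 − f) + 1.2 f s + r f(1 − s)]/1.2

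Example with d = 20%, s = 1/3, f = 0.10. Literal: (0.756 + 0.040)/(1.2 × 0.9333) = 0.796/1.120 = 0.711. Primary with r = 1.2: (0.756 + 0.120)/1.2 = 0.730.

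| d | s | Literal 8.2.4 | Primary, r = 1.2 | Primary, r = 1.02 | Primary, r = 0.84 |
|---|---|---|---|---|---|
| 10% | 1/3 | 0.7052 | 0.7150 | 0.7075 | 0.7000 |
| 10% | 1/2 | 0.7077 | 0.7150 | 0.7075 | 0.7000 |
| 20% | 1/3 | 0.7107 | 0.7300 | 0.7150 | 0.7000 |
| 20% | 1/2 | 0.7158 | 0.7300 | 0.7150 | 0.7000 |

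**4. Reading the table.**

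- Effect lost: literal is lower (more favourable) by 0.007 to 0.019. On the log scale this is ln(0.7150/0.7077) = 0.010 to ln(0.7300/0.7107) = 0.027, or 0.1 to 0.3 SE.
- Effect kept: literal is higher (less favourable) by 0.005 to 0.016.
- Halfway: the sign is mixed.

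Let w be the share of the effect lost after the ICE. Primary exceeds 0.70 by 0.30 f w, and literal exceeds it by 0.30 f s/[1 − f(1 − s)]. Literal is therefore the more favourable when w > s/[1 − f(1 − s)], which is 0.34–0.36 for s = 1/3 and 0.51–0.53 for s = 1/2. Roughly, the share of effect lost must exceed the share of ICEs that are failures.

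**5. Simulation check.** This used 120 negative binomial trials with 5 imputations each, 5% failure and 15% non-failure ICEs, and the effect lost. Mean ratios were 0.722 (primary) and 0.698 (literal), with literal lower in 85% of trials. The formulas give 0.730 and 0.708 for this case, so the gap agrees.

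**6. Keeping non-failure follow-up.** The kept version minus primary is (1.2 − r) f s/1.2, which is never negative for r ≤ 1.2 with equal ICE shares. One exception was found. Suppose 10% of placebo and 5% of brensocatib participants start a chronic antibiotic, the rate is 0.6 afterwards, and 10% per arm have other ICEs with a rate of 1.2 afterwards. The primary is then 0.852/1.170 = 0.728 and the kept version 0.867/1.200 = 0.7225.

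**The case against.** The strongest reply is that 8.2.4 never says that data after other ICEs are excluded. It says what is included and what is set to missing, and the remainder could follow the On-Study default or fall under the general imputation sentence. On either of those readings, with equal ICE shares, the ratio is not more favourable than the primary. This stands to the extent that the loss of data is inferred from silence. It does not remove the point, because the text supports three different datasets and the literal one is the one that fails. The blinded review in SAP 6.2, with its signed report of agreed actions for ICEs, offers a place to settle this before unblinding but does not supply the rule.

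A reader might infer that the analysis is biased in brensocatib's favour. The documents do not support that. The direction turns on ICE mix and post-ICE rates, which they do not give. Someone who stops a baseline antibiotic may still be taking brensocatib, so a return to the placebo rate cannot be presumed. The trigger for the analysis also favours settings with many failure ICEs. With 15% failure and 3% non-failure ICEs, literal gives 0.723, against a primary of 0.714 at the halfway rate and 0.727 if the effect is lost.

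A reader might also infer that 8.2.4 breaks the definitions in Section 2 and 6.7.2, and that this causes the favourable result. Those lists and their treatment-policy rule belong to the Composite Estimand of another endpoint, and the 8.2.4 list is only illustrative. Counting any adverse event sends more brensocatib follow-up to placebo-based imputation, which is the more conservative choice. The wording mismatch is real, but it is a matter of consistency. Only leaving deaths out could push the other way.

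**Conclusion.** The point holds as a gap in specification with a measurable consequence. As written, 8.2.4 gives no place to data observed after non-failure ICEs, and its literal reading discards follow-up that the On-Study estimand uses. The Jump-to-Reference result then cannot be relied on to be at least as demanding as the primary. The possible shift is small, at most about 0.3 SE in the favourable direction in the range examined. That size rests on the assumed ICE shares, mid-year timing, complete follow-up and a full return to the placebo rate. Under a persisting effect the sign reverses.

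The primary analysis is untouched. This analysis is conditional and lies outside the 12 tested hypotheses, and the bidirectional tipping-point analysis in 8.2.2 separately examines missing data.

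**What to change.** Amend SAP 8.2.4 before unblinding:

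- Keep all observed exacerbations and time at risk after ICEs not related to treatment failure, as in the On-Study estimand.
- Set to missing, and impute under Jump-to-Reference, only data after a treatment-failure ICE.
- State whether unobserved time after study withdrawal is also imputed, and under which assumption.
- Replace the illustrative list with one closed treatment-failure list for this analysis. Reconcile its adverse-event wording (any versus treatment-related) and its handling of death due to bronchiectasis with Section 2 and 6.7.2. The narrower 6.7.2 list need not be adopted, because the any-adverse-event wording is the more conservative one here.

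The cost is a few sentences and one data-selection flag; the data are already collected. The change does not guarantee a more conservative result in every case, since an imbalance between arms in antibiotic starts could still move the ratio slightly below the primary. The report should therefore show ICE counts by type and arm next to this analysis.
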